2.8 Can Angiography-derived FFR overcome FLOWER-MI limitations?

The main limitation of the FLOWER-MI trial are: the dilution of FFR deferral by performing a second procedure in all patients and the inability to perform FFR before PCI in 16% of patients and after in 82% of cases. Angiography-derived FFR could overcome all these limitations. In fact, Angiography-derived FFR projections could be acquired during primary PCI and, in case of negative assessment, the patient can avoid a staged procedure. In addition, a virtual PCI plan based on Angiography-derived FFR “pullback” trace can enable operators to obtain a functionally optimized result without the need to repeat the assessment after PCI.

2.9 Novel angiographic measures of plaque composition and vulnerability

Different methods aimed at the estimation of plaque composition and vulnerability have been developed. They are all based on analyses performed on angiography.

2.9.1 Wall shear stress (WSS)

Wall shear stress (WSS) has been associated with atherogenesis and plaque progression. The present study assessed the value of WSS analysis derived from conventional coronary angiography to detect lesions culprit for future myocardial infarction (MI). Three-dimensional quantitative coronary angiography (3DQCA), was used to calculate WSS and pressure drop in 80 patients. WSS descriptors were compared between 80 lesions culprit of future MI and 108 non-culprit lesions (controls).

Endothelium-blood flow interaction was assessed by computational fluid dynamics (10.8 ± 1.41 min per vessel). Median time between baseline angiography and MI was 25.9 (21.9-29.8) months. Mean patient age was 70.3 ± 12.7 . Clinical presentation was STEMI in 35% and NSTEMI in 65%. Culprit lesions showed higher percent area stenosis (%AS), translesional vFFR difference ($\Delta vFFR$), time-averaged WSS (TAWSS) and topological shear variation index (TSVI) compared to non-culprit lesions ($p < 0.05$ for all). TSVI was superior to TAWSS in predicting MI (AUC-TSVI=0.77, 95%CI 0.71-0.84 vs. AUC-TAWSS=0.61, 95%CI 0.53-0.69, $p < 0.001$). The addition of TSVI increased predictive and reclassification abilities compared to a model based on %AS and $\Delta vFFR$ (NRI=1.04, $p < 0.001$, IDI=0.22, $p < 0.001$).

Conclusions: A 3DQCA-based WSS analysis was feasible and can identify lesions culprit for future MI. The combination of area stenoses, pressure gradients and WSS predicted the occurrence of MI. TSVI, a novel WSS descriptor, showed strong predictive capacity to detect lesions prone to cause MI.

2.9.2 Radial Wall Strain (RWS)

The lipid-to-cap ratio (LCR) and thin-cap fibroatheroma (TCFA) derived from optical coherence tomography (OCT) are indicative of plaque vulnerability.

Aims: We aimed to explore the association of a novel method to estimate radial wall strain (RWS) from angiography with plaque composition and features of vulnerability assessed by OCT.

Methods: Anonymised data from patients with intermediate stenosis who underwent coronary angiography (CAG) and OCT were analysed in a core laboratory. Angiography-derived RWSmax was computed as the maximum deformation of lumen diameter throughout the cardiac cycle, expressed as a percentage of the largest lumen diameter. The LCR and TCFA were automatically determined on OCT images by a recently validated algorithm based on artificial intelligence.

Results: OCT and CAG images from 114 patients (124 vessels) were analysed. The average time for the analysis of RWSmax was 57 (39-82) seconds. The RWSmax in the interrogated plaques was 12% (10-15%) and correlated positively with the LCR ($r = 0.584$; $p < 0.001$) and lipidic plaque burden ($r = 0.411$; $p < 0.001$), and negatively with fibrous cap thickness ($r = -0.439$; $p < 0.001$). An RWSmax $> 12\%$ was an angiographic predictor for an LCR > 0.33 (area under the curve [AUC]=0.86, 95% confidence interval [CI]: 0.78-0.91; $p < 0.001$) and TCFA (AUC=0.72, 95% CI: 0.63-0.80; $p < 0.001$). Lesions with RWSmax $> 12\%$ had a higher prevalence of TCFA (22.0% versus 1.5%; $p < 0.001$), thinner fibrous cap thickness (71 μm versus 101 μm ; $p < 0.001$), larger lipidic

plaque burden (23.3% versus 15.4%; $p < 0.001$), and higher maximum LCR (0.41 versus 0.18; $p < 0.001$) compared to lesions with $RWS_{max} \leq 12\%$.

Conclusions: Angiography-derived RWS was significantly correlated with plaque composition and known OCT features of plaque vulnerability in patients with intermediate coronary stenosis.

3 RATIONALE

After the COMPLETE trial², the actual standard of care in the management of STEMI patients with MVD is complete revascularization based on angiography. However, this approach may lead to over- or under-estimation of lesions in a relevant portion of patients with negative impact on prognosis. Invasive physiology has been consistently shown to be superior if compared to angio-guided strategy, but it is underutilized in clinical practice mainly due to feasibility issues.

A functional coronary angiography could overcome the applicability issues related to invasive physiology. In addition, it is particularly appealing in the evaluation of non-culprit lesions since:

- a) It is possible to acquire projection during primary PCI and perform the analysis off-line
- b) In case of negative assessment, the patient can avoid a second procedure to invasively measure physiology
- c) It is possible to optimize most of the procedures by the physiological standpoint through the utilization of the virtual-PCI planner tool pre-PCI without the need to repeat physiology after PCI.
- d) It has been recently shown that if compared to an angio-guided approach, Angiography-derived FFR was able to reduce the incidence of spontaneous MI by 36%

Therefore, a strategy based on functional coronary angiography to indicate and guide PCI could be superior if compared to an angio-guided strategy both from the efficacy (CV death, cerebrovascular accident, MI and ischemia-driven revascularization) and from the safety (BARC 3-5, contrast-associated acute kidney injury) standpoint.

4 STUDY ENDPOINTS

4.1 Primary efficacy endpoint

- Cumulative occurrence of all-cause mortality, cerebrovascular accident, reinfarction, or ischemia-driven revascularization

To test if a complete revascularization based on functional coronary angiography to indicate and guide PCI is superior to an angio-based strategy in the reduction of all-cause mortality, cerebrovascular accident, reinfarction, or ischemia-driven revascularization

4.2 Secondary efficacy endpoints

- CV death and reinfarction (prespecified endpoint for the merged analysis with similar ongoing RCTs on the topic)
- CV death, reinfarction and ischemia-driven revascularization (prespecified endpoint for the merged analysis with similar ongoing RCTs on the topic)
- CV death, cerebrovascular accident, or reinfarction (prespecified endpoint for the merged analysis with similar ongoing RCTs on the topic)
- All-cause mortality
- Cerebrovascular accident
- Ischemic stroke
- Ischemia-driven revascularization
- CV death
- Non-fatal MI
- Spontaneous MI
- Periprocedural MI
- Non-culprit vessel oriented composite endpoint (VOCE) as defined as cardiovascular (CV) death, MI or non-culprit target vessel revascularization (TVR)

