Exclusion criteria	
 1. Planned surgical revascularization 2. Left main as non-culprit lesion 3. Non-cardiovascular co-morbidity reducing life expectancy to < 1 year 4. Any factor precluding 1-year follow-up 5. Prior Coronary Artery Bypass Graft (CABG) Surgery 6. Impossibility to identify a clear culprit lesion 7. Presence of a chronic total occlusion (CTO)
Primary endpoint	
Efficacy: composite of all-cause death, cerebrovascular accident, myocardial infarction, or ischemia-driven revascularization.
 
Safety: composite of contrast-associated acute kidney injury and bleeding BARC 3-5.

Secondary endpoints	
 • CV death • Non-fatal MI • Spontaneous MI • Periprocedural MI • Vessel oriented composite endpoint (VOCE) as defined as cardiovascular (CV) death, MI or non-culprit target vessel revascularization (TVR) • BARC 3-5 • Ischemic stroke • Stent thrombosis • Contrast-induced acute kidney injury • EQ-5D quality of life scale • EQ-5D VAS • Seattle Angina Questionnaire (SAQ) Frequency scale • Quality Adjusted Life Years (QALYs)
Assessment Schedule	
Pre-eligibility screening, primary PCI, randomization, 1 months, 12 months, and every 12 months thereafter.

Study Duration	
Enrolment will occur over approximately 2 years with an expected minimum of 12 months follow-up and an average of approximately 18-24 months follow-up.

[figure not shown]

Clinical Event Adjudication Committee	The following events will be adjudicated by a blinded Clinical Event Adjudication Committee: death, myocardial infarction, resuscitated cardiac arrest, hospitalization for unstable angina, hospitalization for heart failure, and stroke.
Data and Safety Monitoring Board	An independent Data and Safety Monitoring Board will advise the study leadership on safety aspects and overall progress of the study.

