Recently, a retrospective post hoc Angiography-derived FFR analysis of untreated nontarget vessels (any degree of diameter stenosis [DS]) was performed from the randomized multicentre COMFORTABLE AMI (Comparison of Biolimus Eluted From an Erodible Stent Coating With Bare Metal Stents in Acute ST-Elevation Myocardial Infarction) trial by assessors blinded for clinical outcomes. The primary end point was cardiac death, spontaneous nontarget vessel myocardial infarction, and clinically indicated nontarget vessel revascularization (ie, $\geq 70\%$ DS by 2-dimensional quantitative coronary angiography or $\geq 50\%$ DS and ischemia) at 5 years. Of 1161 patients with ST-segment-elevation myocardial infarction, 946 vessels in 617 patients were analyzable by Angiography-derived FFR. At 5 years, the rate of the primary end point was significantly higher in patients with Angiography-derived FFR ≤ 0.80 (n=35 patients, n=36 vessels) versus Angiography-derived FFR > 0.80 (n=582 patients, n=910 vessels) (62.9% versus 12.5%, respectively; hazard ratio [HR], 7.33 [95% CI, 4.54-11.83], $P < 0.001$), driven by higher rates of nontarget vessel myocardial infarction (12.8% versus 3.1%, respectively; HR, 4.38 [95% CI, 1.47-13.02], $P = 0.008$) and nontarget vessel revascularization (58.6% versus 7.7%, respectively; HR, 10.99 [95% CI, 6.39-18.91], $P < 0.001$) with no

significant differences for cardiac death. Multivariable analysis identified Angiography-derived FFR ≤ 0.80 but not $\geq 50\%$ DS by 3-dimensional quantitative coronary angiography as an independent predictor of the primary end point. Results were consistent, including only $>30\%$ DS by 3-dimensional quantitative coronary angiography¹⁴.

In conclusion, Angiography-derived FFR evaluation is feasible in STEMI setting and its value is associated with long-term outcome.

2.6 FAVOR III: Angiography-derived FFR utilization significantly reduces MI vs angio-guided revascularization

Angio-guided revascularization was the strategy utilized in the COMPLETE trial and recent other trials questioned the superiority of invasive physiology through FFR over the traditional angio-based eyeballing^{15,16}

[figure not shown]

Figure 2: Kaplan-Meier curves for the primary (A) and major secondary (B) endpoints in the intention-to-treat population. MACE=major adverse cardiac events. QFR=quantitative flow ratio.

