7.2 Conventional angiography guided complete revascularization

[figure not shown]
[figure not shown]
All patients randomized to angio-guided revascularization must undergo PCI of all non-culprit lesions angiographically deemed $\geq 50\%$. Complete revascularization must be obtained within index hospitalization.

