7.3 Functional coronary angiography complete revascularization

Patients who are randomized to this strategy will receive revascularization of the culprit lesion and functional coronary angiography evaluation on all non-culprit lesions (angiographically deemed $\geq 50\%$) and revascularization of all-functional positive lesions according to angio-FFR based virtual PCI plan. Functional evaluation is mandatory for all stenosis. When angiography-derived FFR is not feasible with any of the available tools, then a staged procedure to perform invasive FFR is mandatory. According to available literature, the overall rate of invasive FFR should not exceed 5% of the patients. PCI of vessel with negative functional evaluation is considered a protocol violation. Revascularization of the positive (at angiography-derived FFR assessment) non-culprit lesions must be performed within the index hospitalization.

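### The non-culprit VOCE never says what makes a vessel a target; if it means treated by PCI, later revascularization of a deferred vessel goes uncounted, and only in AIR

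*Protocol*

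**What the plan says.** Section 4.2 lists, among the secondary efficacy endpoints, a VOCE labelled as non-culprit and made up of "cardiovascular (CV) death, MI or non-culprit target vessel revascularization (TVR"). The synopsis has the same components under a slightly different label: "Vessel oriented composite endpoint (VOCE) as defined as cardiovascular (CV) death, MI or non-culprit target vessel revascularization (TVR"). Section 8 defines MI, death, ischemia-driven revascularization, stent thrombosis, stroke, kidney injury and bleeding, but neither the VOCE nor target vessel.

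The set of treated vessels differs by arm:

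- **ANGIO (7.2):** patients "must undergo PCI of all non-culprit lesions angiographically deemed" at least 50%.
- **AIR (7.3):** the rule is "revascularization of all-functional positive lesions according to angio-FFR based virtual PCI plan", and "PCI of vessel with negative functional evaluation is considered a protocol violation".
- **AIR (7.3.1.2):** functionally negative vessels above a plaque-vulnerability threshold go to PCI; the others receive medical therapy.

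**The concern.** A vessel-oriented composite compares the arms fairly only if the vessels that can have an event are fixed before treatment is decided. Here the deciding word, *target*, has two possible meanings. Under one, a target is any non-culprit vessel with a qualifying lesion, and the list is the same whichever arm the patient is in. Under the other, a target is a vessel that received PCI, and the list is a consequence of allocation. Qualifying vessels left untreated by design exist only in AIR, so under the second meaning the endpoint drops events from that arm alone. The dropped events are later procedures on vessels that were deferred.

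The VOCE is one of the secondary endpoints for which section 9 promises formal type I error control, with one-sided tests for superiority of the functional strategy. A difference produced by the counting rule would act in the direction being tested.

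**Working it through.** **1. Which vessels can contribute a revascularization event**

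| Non-culprit vessel with a lesion of at least 50% | Target = treated by PCI | Target = any qualifying vessel |
|---|---|---|
| ANGIO (all treated, 7.2) | counts | counts |
| AIR, treated | counts | counts |
| AIR, deferred | does not count | counts |

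Only the third row separates the two readings, and by design it exists in one arm only.

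**2. Is the treated-vessel reading realistic?** The other uses of a VOCE in the protocol concern vessels that had PCI: the post-stenting cohort and the post-PCI analysis in 2.4, and the virtual-PCI trial in 2.7, in which both arms received PCI. Section 8.3, by contrast, defines ischemia-driven revascularization by the lesions that led to enrolment, treated or not. That treatment-neutral wording was available and the VOCE does not use it.

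**3. Illustrative number of uncounted events.** The protocol gives no VOCE rate, non-culprit revascularization rate or deferral rate for this trial, so there is no planned figure to reproduce. The inputs are:

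- 35% of non-culprit lesions positive by angiography-derived FFR in the STEMI cohort in 2.5, so 65% negative. Assumption: the lesion share carries over to patients, 0.65 × 900 = 585.
- 7.7% nontarget-vessel revascularization at 5 years in patients with values above 0.80 (2.5). Assumption: even accrual, 7.7% / 5 = 1.54% per year.
- Follow-up of 17 months (middle of the 16–18 months in 9.1), or 23 months, which is what even recruitment over 22 months plus 12 months gives (12 + 22/2).

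Results:

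- 17 months: 1.54% × 17/12 = 2.18%; × 585 = 12.8, about 13 events.
- 23 months: 1.54% × 23/12 = 2.95%; × 585 = 17.3, about 17 events.
- Plaque rule: 2.9.2 reports a maximum radial wall strain of 12% (10–15%) in a cohort with intermediate stenosis, and the threshold in 7.3.1.2 is above 12%. If 12% is a median and applies here, about half the negative vessels would go to PCI: 12.8/2 = 6.4 and 17.3/2 = 8.6, roughly 6 to 9 events, before the second plaque criterion.

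As a share of 900 patients these are 1.4 to 1.9 percentage points, or 0.7 to 1.0 with the plaque rule.

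**4. Effect on the comparison if the arms truly do not differ.** Let *b* be the rate of CV death or MI, *r* the non-culprit revascularization rate, and *f* the share of AIR revascularizations that fall on deferred vessels. Ignoring overlap between components, ANGIO shows *b + r* and AIR shows *b + r*(1 − *f*). Assumed ranges: *b* 4–6%, *r* 2–4%, *f* 20–65%, with 859 per arm (1718/2), one-sided 5%, pooled-variance test.

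- Mildest case (*b* 6%, *r* 2%, *f* 20%): 8.0% against 7.6%, ratio 0.95; chance of a nominally significant result for AIR 9%.
- Most severe case (*b* 4%, *r* 4%, *f* 65%): 8.0% against 5.4%, ratio 0.68; chance 70%.
- Any qualifying vessel counted: ratio 1.00, chance 5%.

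The loss assumed here runs from 0.02 × 0.20 = 0.4 to 0.04 × 0.65 = 2.6 percentage points, which brackets the figures in step 3.

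**The case against.** The case against is substantial, and most of it stands as a limit on the point.

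- **The bias follows from one reading only.** The label in 4.2, non-culprit vessel oriented, fits a list of all qualifying non-culprit vessels. On that reading nothing is wrong. This stands.
- **Section 2.5 does not settle the meaning.** A reader might infer it from "Angiography-derived FFR analysis of untreated nontarget vessels", but that phrase summarizes a post hoc analysis of a cited stent trial. If nontarget already meant untreated, the first adjective would be redundant. It shows that the usage occurs, not that 4.2 adopts it.
- **The endpoint is not blind to harm from deferral.** A reader might infer that too. The VOCE counts any MI and any CV death, so an infarction from a deferred vessel counts on either reading. Ischemia-driven revascularization of an enrolling lesion, deferred or not, is in the primary endpoint (4.1), stands alone in 4.2, and is split into culprit and non-culprit by 8.3.
- **The event counts are soft.** They turn a lesion proportion into a patient proportion. The 7.7% comes from vessels with any degree of stenosis under a different revascularization definition, so it could be too low for lesions of at least 50%. In the other direction, patients who also have an MI score in the VOCE anyway.
- **The definition may exist elsewhere.** Section 7.9 refers to an adjudication charter and section 9 to a detailed analysis plan, neither shown. But 5.5 says events are adjudicated on definitions set out in the protocol itself, and this one is not among them.

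What survives is that the protocol fixes an endpoint with a word whose two readings give different event counts, and only one of them treats the arms alike.

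**Conclusion.** The point holds conditionally. If *target* means treated by PCI, the revascularization part of this one secondary endpoint favours AIR through the counting rule alone. If it means every qualifying non-culprit vessel, there is no bias. The documents do not say which applies, so they do not support a flat statement that the VOCE favours AIR. Nor is every non-culprit vessel in ANGIO a target on the first reading: only those with a lesion of at least 50% must be treated.

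The size cannot be established from the documents. The 13 to 17 uncounted events, or 6 to 9 with the plaque rule, are illustrations that rest on the lesion-to-patient extrapolation and even accrual. The apparent ratios of 0.95 to 0.68 rest wholly on assumed rates. The deferral rate is itself uncertain because 7.3 calls PCI of a functionally negative vessel a violation while 7.3.1.2 directs PCI of some of them; these sections must be reconciled.

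The primary endpoint and the stand-alone ischemia-driven revascularization endpoint are untouched. The change is worth making because it costs little and removes a possible arm-dependent bias.

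**What to change.** In 4.2, the synopsis and the adjudication definitions, replace non-culprit target vessel revascularization with: *revascularization of any non-culprit vessel that had a qualifying (≥50%) lesion at randomization, whether treated or deferred*. Record the list of these vessels for each patient at randomization and use it unchanged in both arms. If the charter or analysis plan already defines the term this way, carry that wording into the protocol.

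The CV death and MI components can stay as they are, and the event need not be narrowed to ischemia-driven procedures. Tying MI to a vessel is a matter of preference and is not needed to remove this problem.

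The cost is a wording change plus a baseline vessel list. Details of the cardiovascular anatomy are already recorded in the eCRF at screening (5.3), and the core lab already reviews all angiograms and percent stenosis (section 12). The downside is that AIR may show more VOCE events than under the treated-vessel reading. The definition should be settled before any comparison by arm is seen.

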4.3 Primary safety objective

- Cumulative occurrence of contrast-associated acute kidney injury and bleeding BARC 3-5

To test if a complete revascularization based on functional coronary angiography to indicate and guide PCI is superior to an angio-based strategy in the reduction of BARC 3-5 and contrast-associated acute kidney injury

4.4 Exploratory endpoints

- Quality of life measured with EQ-5D quality of life scale
- Angina symptoms control measured with Seattle Angina Questionnaire (SAQ) Frequency scale
- Quality Adjusted Life Years (QALYs)
- Cost effectiveness and cost utility

[figure not shown]
- Number of repeated procedures during index hospitalization

5 STUDY DESIGN, SCREENING AND RANDOMIZATION

5.1 Study design

All comers, prospective, randomized, multicenter, open-label trial with blinded adjudicated evaluation of outcomes (PROBE).

5.2 Study flow chart

5.3 Screening

All patients undergoing CAA because of STEMI must be screened for eligibility. Patient’s eligibility must be assessed after the evidence of multivessel disease at CAA amenable for PCI with a clear culprit lesion. Successful culprit lesion treatment must be obtained in all patients before randomization. Screening, eligibility and randomization must be performed within 48 hours from the primary PCI and successful treatment of culprit lesion. After eligibility is confirmed, written informed consent must be obtained prior to randomization. Key baseline patient characteristics (i.e., inclusion/exclusion criteria, demographics, medical history, details of cardiovascular anatomy, ECG and laboratory test results) will be recorded on the electronic Case Report Forms (eCRF). All CAA from the initial qualifying PCI as well as all functional assessments will be collected and forwarded to an angiographic core lab for further assessment.

5.4 Randomization

Randomization will be performed after CAA and culprit lesion treatment. Randomization will be performed centrally using an internet-based system. The patient identification number (Patient ID) and the treatment allocation will be assigned by the central randomization system. Treatment allocation will be assigned according to a computer-generated randomization list stratified by center. Randomization will also be stratified by sex (male vs. female), age (≤ 75 years vs. > 75 years) and non-culprit vessel location (left

anterior descending artery vs. non left anterior descending artery). All patients who are randomized are irrevocably in the study, whether or not they are subsequently found to be eligible, or actually receiving the allocated treatment. Therefore, all patients must be followed until the pre-specified study end date.

